### 10.3 Additional statistical matters

There is no provision for interim analysis and no criteria for early termination of the clinical investigation on statistical grounds.

Any deviations from the statistical plan provided in this protocol will have to be approved by the sponsor and the reasons for the deviation reported in the clinical investigational report. Dropouts and withdrawn participants will

be included in the data analysis for the procedures that they completed. They will be grouped together and compared to the group that finished the protocol. Any statistical differences of the two groups will be reported. If the participants have not provided any data, they will not be included in the data analysis. No particular information will be excluded from the statistical analysis and tests, as described above.

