**Table 4 Endpoints, test methods and hypotheses**

	Hypothesis	Test Method	Endpoint	Acceptance Criteria
A	Subjects reduced exertion performing 6MWT compared to previous prosthesis (primary outcome)	BORG scale	Mean difference in BORG score pre and post 6MWT compared to comparator	$H_0: \mu_1 \leq \mu_2$ $H_1: \mu_1 > \mu_2$ $p<0.05$
B	Subjects improved performance in 6MWT compared to previous prosthesis.	6MWT (meters)	Average distance walked in 6MWT compared to comparator	$H_0: \mu_1 \geq \mu_2$ $H_1: \mu_1 < \mu_2$ $p<0.05$
C	Subjects report on average no worse support in sit to stand and stand to sit than with previous prosthesis.	Self-report: PMQ (Questions 9 and 10) Likert scale 0-4	Total score of PMQ questions 9 and 10 compared to comparator	$H_0: \mu_1 \geq \mu_2 +  M_{NI} $ $H_1: \mu_1 < \mu_2 +  M_{NI} $ $ M_{NI}  = 1$ $p<0.05$
D	Subjects perceived safety in hill descent is no worse than with previous prosthesis.	Self-report: Modified PEQ 14F (rate your safety when walking down a steep hill using the prosthesis) Likert Scale 1-10	Average score compared to comparator	$H_0: \mu_1 \geq \mu_2 +  M_{NI} $ $H_1: \mu_1 < \mu_2 +  M_{NI} $ $ M_{NI}  = 1$ $p<0.05$
E	Subjects perceived safety in stair descent is no worse than with previous prosthesis.	Self-report: Modified PEQ 13D (rate your safety when walking downstairs using the prosthesis) Likert Scale 1-10	Average score compared to comparator	$H_0: \mu_1 \geq \mu_2 +  M_{NI} $ $H_1: \mu_1 < \mu_2 +  M_{NI} $ $ M_{NI}  = 1$ $p<0.05$
F	Subjects perceive no speed limitation while walking with the investigational device.	Self-report(yes/no): „Are you satisfied with your walking speed using your prosthesis/test prosthesis?”  Support question: “Do you feel that your walking speed is limited by your prosthesis/test prosthesis?”	Proportion of subjects (p) reporting satisfaction with walking speed on investigational device.	$H_0: p < 80\%$ $H_1: p \geq 80\%$ $p<0.05$

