G	Subjects reported ability to ambulate over typical environmental obstacles with the investigational device is no worse than with previous prosthesis.	Self-report: PMQ (Question 2-7) Likert scale 0-4 PLUS M	Total score of PMQ questions 2-7 and PLUS M T-score compared to comparator.	For PLUS-M: $H_0: \mu_1 \geq \mu_2 +  M_{NI} $ $H_1: \mu_1 < \mu_2 +  M_{NI} $ $ M_{NI}  = 10T$ For PMQ questions: $H_0: \mu_1 \geq \mu_2 +  M_{NI} $ $H_1: \mu_1 < \mu_2 +  M_{NI} $

				$ M_{NI}  = 3$ $p < 0.05$
H	Subjects safe and stable stance phase perception no worse than previous prosthesis.	Self-report: Modified PEQ 13A (rate your safety (during stance phase) when walking with your prosthesis/test prosthesis) Likert Scale 1-10	Average score compared to comparator	$H_0: \mu_1 \geq \mu_2 +  M_{NI} $ $H_1: \mu_1 < \mu_2 +  M_{NI} $ $ M_{NI}  = 1$ $p < 0.05$
I	Provides comfort in standing no worse than previous prosthesis.	Self-report: PEQ-Question 1D “Rate your comfort while standing when using your prosthesis/test prosthesis” Likert Scale 1-10	Average score compared to comparator	$H_0: \mu_1 \geq \mu_2 +  M_{NI} $ $H_1: \mu_1 < \mu_2 +  M_{NI} $ $ M_{NI}  = 1$ $p < 0.05$
J	The investigational device provides easier setup for CPO compared to previous version of power knee	Self-report: Likert Scale 1-10	Average score compared to previous versions of PK	$H_0: \mu_1 \geq \mu_2$ $H_1: \mu_1 < \mu_2$ $p < 0.05$
K	The investigational device provides no worse ease of setup for CPO compared to SOTA passive MPKs	Self-report: Likert Scale 1-10	Average score compared to SOTA MPKs	$H_0: \mu_1 \geq \mu_2 +  M_{NI} $ $H_1: \mu_1 < \mu_2 +  M_{NI} $ $ M_{NI}  = 1$ $p < 0.05$
M	The investigational device provides acceptable noise level	Self-report: PEQ- Questions 3K, 3L Likert Scale 1-10 Support question (yes/no) “Would the noise from the test device prevent you from preferring it as your usual prosthesis?”	Proportion of participants (p) with average score of PEQ 3K & 3L over 5 with investigational device.	$H_0: p < 80\%$ $H_1: p \geq 80\%$ $p < 0.05$

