## 8.3 Subjects

All subjects will be dispositioned as follows:

- Screen Failure: Subject did not pass screening procedures, not called in for clinical visit;
- Candidate for enrollment: Passed screening procedures, accepts to come in for clinical visit;
- Enrolled: Subject signs informed consent;
- Fitted: Subject leaves the clinic on the investigational device;
- Discontinued: Candidate for enrollment or Enrolled subject whose participation ended because they withdrew consent, were withdrawn by the Investigator, were lost to follow up, or died;]

Table 5 Inclusion/Exclusion criteria

Inclusion:	Exclusion:
Only patients with the following characteristics are eligible for study entry:	Patients with the following characteristics are not eligible for study entry:
50Kg < body weight < 116Kg	50Kg > body weight > 116Kg
K3-K4 amputees with unilateral transfemoral amputation or knee disarticulation	Bilateral amputees
Allows for 37mm knee center height to dome of pyramid alignment	Users with socket problems
Currently using a MPK or Power Knee	Users with co-morbidities in the contra-lateral limb, which affect their functional mobility
Older than 18 years old	Younger than 18 years old
No socket issues/changes in the last 6 weeks and no socket changes expected during the duration of the study period.	Users with stump pain
Comfortable and stable socket fit	Users with cognitive impairment
Willing and able to participate in the study and follow the protocol	Users involved in other clinical tests and/or receiving treatment that the testing might affect.

A subject can withdraw from participation at any time, at his/her discretion, and this will not have any consequences for the participant's treatment. In such cases a report stating reasons for discontinuation of the participant shall be prepared by the PI, if the participant wants to disclose those reasons. No further investigational procedures concerning the subject will be conducted, except for a statement explaining the reason for withdrawal (if disclosed), including but not limited to: interacting or interviewing the subject in order to obtain data on him/her; obtaining additional private information on the subject by either observing the subject or collecting or receiving such information from any source.

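### Table 4 rows F, L (L-test) and M (noise): a fitted subject who withdraws because of the knee before its test visit is left out of the proportion judged against 80%

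*Combined protocol and SAP*

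**What the plan says.** Three secondary criteria in Table 4 are one-sample proportions on the investigational knee, each with an 80% bar at the 0.05 level:

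- Row F: "Proportion of subjects (p) reporting satisfaction with walking speed on investigational device".
- Row L, second part: the share who complete the L-test using the gait functions.
- Row M (noise; the letter M is used twice in the table): the share whose average of PEQ items 3K and 3L exceeds 5. A yes/no support question accompanies it, "Would the noise from the test device prevent you from preferring it as your usual prosthesis", but the PEQ average is the endpoint.

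None of these rows states who is in the denominator.

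Section 10.3 says that dropouts and withdrawn participants will "be included in the data analysis for the procedures that they completed". It adds: "If the participants have not provided any data, they will not be included in the data analysis". On dropouts as a group it says: "They will be grouped together and compared to the group that finished the protocol", with any differences reported.

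Section 8.3 says that after withdrawal "No further investigational procedures concerning the subject will be conducted", apart from recording the reason if the subject discloses it. The same section defines a disposition that could serve as a denominator: "Fitted: Subject leaves the clinic on the investigational device".

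Under section 8.4 and Table 6, the first questionnaires and L-test on the investigational knee come at the end of its 2-3 week period: Visit 2 for Group 1 and Visit 3 for Group 2.

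**The concern.** These three rows ask whether the knee is acceptable: fast enough, usable in its gait functions, quiet enough. A subject who takes it home and withdraws because it is not has answered at least one of those questions in the negative. Under the completed-procedures rule that subject has no value for any of the three rows and disappears from numerator and denominator alike. The loss can only push the proportions up.

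The case is foreseeable. Section 8.3 itself provides for withdrawal caused by problems with the device. It also lets the local investigator withdraw a participant at any time without pre-specified criteria, and section 9 says that subjects are not blinded. With about 15 subjects against an 80% bar, a single excluded failure can decide whether a criterion is met. Choosing the denominator after the data are seen could do the same.

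**Working it through.** **Where 15 and 18 come from.** Section 10.2 gives dz = 0.7084529, one-sided alpha 0.05, and a Wilcoxon signed-rank test by the A.R.E. method with a normal parent distribution. With N = 15:

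- n′ = 15 × 3/π = 14.324, so df = 13.324
- δ = 0.7084529 × √14.324 = 2.681
- critical t = 1.768, power = 0.815

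This reproduces the plan's output. The 18 is 15 × 1.2. Both figures were derived for the primary endpoint and are used here only as plausible denominators.

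**Who is lost from rows F, L (L-test) and M (noise)**

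| Time of withdrawal | Group 1 | Group 2 |
|---|---|---|
| Visit 1 to Visit 2 | Fitted, no device value: left out | Not yet fitted: not relevant |
| Visit 2 to Visit 3 | Device value already recorded | Fitted, no device value: left out |

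Each subject is exposed in only one of the two intervals.

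**Effect on the test.** Section 10.1 names only a paired t-test and the Wilcoxon test, neither of which applies to a single proportion. I assume a one-sided exact binomial test, following the directional hypotheses in Table 4: p-value = P(X ≥ k) for X ~ Bin(n, 0.80).

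| Situation | k/n | Proportion | p-value | Met at 0.05? |
|---|---|---|---|---|
| Leavers left out, all 15 tested succeed | 15/15 | 100% | 0.80^15 = 0.035 | Yes |
| One device-related leaver counted as failure | 15/16 | 94% | 0.141 | No |
| Two | 15/17 | 88% | 0.310 | No |
| Three (worst case) | 15/18 | 83% | 0.501 | No |

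At every n from 14 to 18 the test is met only if all analysed subjects succeed (14/14 p = 0.044; 18/18 p = 0.018). One failure who attends and is counted also loses it (14/15 p = 0.167; 17/18 p = 0.099).

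**Other side of the test.** A two-sided exact test adds the lower-tail outcomes that are no more likely than 15/15, namely X ≤ 8: 0.035 + 0.018 = 0.053. The criterion then fails at 15/15 as well, so the exclusion reverses nothing at 15.

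**Chance of passing when true success is exactly 80%.** Let w be the assumed share of failures who withdraw before the test visit. The chance is the sum of the trinomial probabilities (success, failure attending, failure gone) over outcomes that pass the one-sided test.

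| w | 18 fitted, leavers left out | 15 fitted, leavers left out |
|---|---|---|
| 0 | 0.018 | 0.035 |
| 0.25 | 0.054 | 0.068 |
| 0.5 | 0.144 | 0.101 |
| 0.75 | 0.341 | 0.134 |
| 1 | 0.716 | 0.167 |

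With leavers counted as failures, the chance stays at 0.018 (18 fitted) and 0.035 (15 fitted) throughout. The values of w are assumptions; the documents give nothing from which to estimate them.

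**The case against.** Five points can fairly be made for the plan.

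1. **No sentence excludes failures by name.** The exclusion follows from the completed-procedures rule, the end of procedures at withdrawal, and an undefined denominator. That is correct, and a reader who concludes that device failures can never count goes too far. A subject who attends and reports failure is counted. So is one who stops wearing the knee but still attends, since section 8.3 ends procedures on withdrawal from the study, not on stopping use.

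2. **Device-related withdrawals would be visible.** Section 10.3 compares dropouts with finishers, reasons are recorded where disclosed, and section 8.3 seeks permission to follow device-related withdrawals. This stands as transparency. It does not alter the proportions, and these subjects have no device values on the three rows to compare.

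3. **The planned losses need not matter.** A reader might infer that the three losses between 18 and 15 turn a pass into a fail. The documents do not support that. Nothing says these losses are device-related or fall between fitting and the device test visit. If losses fell evenly over the two intervals, about half would lie outside that window.

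4. **The reversal depends on an assumed test and on complete success among those tested.** This stands. The two-sided result at 15/15 shows the first part and 14/15 the second. If the 80% bar were read as a bare point estimate, 15/18 (83%) would still clear it.

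5. **A withdrawal is not a failure on every row.** Someone who leaves because of noise has not thereby failed the L-test, and an undisclosed reason may be unrelated. This stands and shapes the fix: undisclosed reasons belong in a sensitivity result, not in the main count of failures.

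**Conclusion.** The concern holds as a matter of direction and rule. For these three secondary criteria, the plan leaves out fitted subjects who withdraw for a device-related reason before the device test visit, and nothing in it puts them back. The bias is upward.

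Its size is conditional. Under the assumed one-sided exact test and with all 15 tested subjects succeeding, one such withdrawal is enough to change the decision (p = 0.035 to 0.14); p = 0.50 is the worst case, not an expectation. If every loss is unrelated to the device or falls outside the window, the results are unchanged. It would also be wrong to infer that the primary result is at risk: the Borg comparison and its sample size do not depend on these proportions.

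**What to change.** Before data are seen, amend Table 4 rows F, L (L-test) and M (noise), and section 10.3, as follows:

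- **Denominator:** all subjects with disposition 'Fitted', except those lost before the device test visit for a documented reason unrelated to the device.
- **Failures:** count as not successful any subject who withdraws before that visit for a device-related reason.
- **Undisclosed reasons:** state their handling explicitly. The consistent choice is to leave them out of the main proportion and count them in the worst case below.
- **Test:** name it, for example a one-sided exact binomial test against 80%.
- **Sensitivity results:** report (a) the as-observed proportion and (b) a worst case in which losses with an undisclosed reason also count as not successful.

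The cost is wording only. The disposition category and the recording of reasons already exist, and no visits, data or subjects are added. The three criteria become slightly harder to meet, and a subject who left for one device reason is counted as not successful on all three rows, which is stricter than the evidence for the other two. The as-observed result lets a reader see how much that matters.

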## 11 Amendments and Deviations from the Protocol (CIP)

---

### 11.1 Amendments

Any amendments to this protocol must be first approved by the sponsor and PI for single site studies, and then be evaluated by the IRB and, where appropriate regulatory authorities, before being implemented.

For non-substantial changes (e.g. minor logistical or administrative changes, change of monitor(s), telephone numbers, renewal of insurance) not affecting the rights, safety and well-being of human subjects or not related to the clinical investigation objectives or endpoints, a simple notification to the IRB and, where appropriate, regulatory authorities can be sufficient.

### 11.2 Deviations

Investigators are not allowed to deviate from this protocol without a formal approval from the IRB, if the deviation affects subject's rights, safety and wellbeing, or the scientific integrity of the clinical investigation. Any such deviation from the protocol is to be documented in detail and the report sent to the IRB.

Under emergency circumstances, deviations from the protocol to protect the rights, safety and well-being of human subjects may proceed without prior approval of the sponsor and the IRB. Such deviations shall be documented and reported to the sponsor and the IRB as soon as possible.

Investigators can request for an approval from the sponsor for a deviation if the deviation does not affect subject's rights, safety and wellbeing, or the scientific integrity of the clinical investigation.

In case of a deviation from this protocol taking place without prior approval from the sponsor, and IRB/REB/REC as applicable, it shall be reported to the sponsor within 24 hours of LPI knowledge of the deviation. The LPI responsible for the deviation is to send a report to the sponsor no later than five days after the deviation was reported. The report shall include:

- Reason for deviation
- When deviation took place
- Circumstances of the event
- Identification of all subjects affected by the deviation, if any
  - Details how each subject is affected, e.g. rights, safety or wellbeing
- Details how this deviation might affect the scientific integrity of the clinical investigation

The sponsor and the IRB/REB/REC will evaluate any deviations that take place without prior approval on a case-by-case basis. If the deviation affects subject's rights, safety and wellbeing, and the scientific integrity of the clinical investigation the LPI shall be disqualified from further participation in the clinical investigation.

## 12 Statement of Compliance

---

The clinical investigation is sponsored by Össur Iceland ehf.

It shall be conducted:

- in accordance with the ethical principles that have their origin in the Declaration of Helsinki
- in compliance with the ISO 14155 International Standard
- in compliance with any regional or national legislations, as applicable

The clinical investigation shall not commence until the required approval from the IRB, and regulatory authority as applicable, has been obtained.

Any additional requirements imposed by the IRB or regulatory authority shall be followed, as applicable.

## 13 Ethical Considerations

### 13.1 Anticipated clinical benefits

A patient using the investigational device may or may not benefit clinically from using the device as opposed to using another **MPK prosthesis** commercially available. Compared to not using a **MPK prosthesis** the patient will benefit significantly in terms of mobility and ability to live independently. Further on the user will be trained on a new prosthetic component to experience the unprecedented functionality of the new component to mitigate the known deficiencies associated with his amputation. Within the test he/she will be trained on restoring physiological movement pattern closer to those of non-amputees.

Anticipated benefits include, among others: improved step-over-step ramp navigation; reduced effort to sit/stand and reduce likelihood of falls. See chapter 6 for details.

Additionally, the benefit for the user during the testing is that he/she helps in developing a new **MPK prosthesis**.

### 13.2 Device related risk

Each device designed and manufactured by Össur is subjected to thorough risk assessment, analysis and control, with failure mode effect analysis and hazard analysis, according to QM1673 Risk Management process, based on ISO 14971 (Risk Management for Medical Devices). All changes performed to the software and/or functions of a device are submitted to multi-level verification and, as applicable, validation processes before being authorized for use in a clinical investigation.

The FMEA and hazard analysis are tools for identifying harms, the sequence of events, their probability, and the potential failures that can cause these harms. Anticipated adverse device effects and residual risks associated with the investigational device, are identified in the **Hazard Analysis Documentation [3]** and **Chapter 7 in the Clinical Investigator's Brochure [4]**.

The Hazard analysis document [3] contains analysis on foreseeable adverse events and anticipated adverse device effects, together with their likely incidence, mitigation or treatment.

Reasonably foreseeable misuses:

- Use of product by user exceeding the maximum user weight.
- Use of the product by user exceeding the activity or impact levels specified above.
- Use of the product for sport activities.
- Submersion of the product in water or exposure to quantity of water exceeding what is considered normal weather.
- Failure to properly maintain the product and/or maintain the product to the expected level of cleanliness.
- Product contamination by foreign substances or operation of the product in dirty or dusty environments.
- Failure to follow recommended or mandatory service schedule.
- Use of the product over the specified maximum life duration.

### 13.3 Risk of Study (To Patient)

At each visit a PI/CI, a certified CPO/CO/CP or clinician, will be present to ensure the safety of the participants. The study adds no additional risk other than the risks identified above. Subjects will use the trial device as their primary prosthesis in the same manner as they would normally do on their prescribed prosthesis. Thus, they are not required to do anything different from their routine clinical visit for acquiring a new **MPK prosthesis and their daily living activities between study visits**.

## 13.4 Risk Mitigation

For each device designed by Össur risk mitigation is part of the design process according to ISO 14971 [3]. Furthermore, each participant fitted with a **MPK prosthesis** for the first time, **or an upgraded/adjusted version of the device**, will be trained by a fully qualified professional until the user can demonstrate sufficient understanding of the product operation and demonstrate minimum ability level in its operation. This process is the same as the usual training process deployed for normal fitting of a **MPK prosthesis**.

As part of the training process, the participant will be informed on the risks inherent in using a **MPK prosthesis in an uncontrolled environment**. Moreover, the participant will be provided with the product literature (e.g. Information for User), as well as being informed and trained on how to use the product.

## 13.5 Risk-to-Benefit Rationale

The development of a MPK prosthesis is controlled by a multi-level verification and validation processes before being authorized for field testing and subsequent release. The Design & Verification process execution, coupled with the risk management and control strategy deployed for POWER KNEE MAINSTREAM – Dynamic ensure that the risks associated with use of the device in typical daily living conditions does not exceed risks level associated with the operation of any such device under similar conditions.

The residual risks of the investigation and the investigational device are minimal and are significantly outweighed by the benefits of participating in the investigation.

